## 7.0 PROTOCOL DEVIATIONS

Protocol deviations will be presented by subject in a data listing. Subjects with protocol deviations will be listed individually, including subject number and observed deviation. Number and percentage of subjects with each type of protocol deviation will be summarized by site for individual treatment group and overall, as appropriate, for the ITT population.

Depending on the seriousness of the deviation, subject might be excluded from the PP population, which shall be documented prior to database lock. [REDACTED]

## 8.0 DEMOGRAPHIC AND BASELINE CHARACTERISTICS

### 8.1 Demographic and Baseline Characteristics

Demographic endpoints, baseline assessments, and subject characteristics will be presented based on the ITT population using descriptive statistics by treatment, as appropriate. The variables to be summarized are described below:

- Continuous variables
  - Age (years)
  - Body Mass Index (BMI) (kg/m^2)
- Categorical variables
  - Sex (Female, Male)
  - Race (White, Black or African American, Asian, American Indian or Alaska Native, Native Hawaiian or Other Pacific Islander, Other)

Ethnicity (Hispanic or Latino, Not Hispanic or Latino)

Fitzpatrick Skin Types (FST) (I, II, III, IV, V, VI)

FST is a skin classification system that categorizes different skin colors, and their reactions to ultraviolet light. [REDACTED]

[REDACTED]

Demographic and baseline characteristics will be presented by treatment and subject in data listings.

## 8.2 Medical History

History of relevant surgical events and medical conditions, including any prior dermatological procedures or implants, are collected.

Medical history will be summarized by individual treatment group and overall, as appropriate, for the ITT population as given below:

- i) Medical history for each body system including number of events, number of subjects (n) and percentage (%).
- ii) Medical history occurring in  $\geq 2\%$  of subjects.
- iii) Allergy history for each body system including number of events, number of subjects (n) and percentage (%).
- iv) Cosmetic/Aesthetic Procedures and Implant History including number of procedures, number of subjects (n) and percentage (%).

Medical history, Allergy history, and Cosmetic/Aesthetic Procedures and Implant History information will be reported by treatment and subject in separate data listings.

## 9.0 EFFECTIVENESS VARIABLES

### 9.1 Primary Effectiveness Variable

Change from baseline in the blinded evaluator (BE) live assessment of midface fullness, for the right and left side of the face, at 12 weeks after the last injection, [REDACTED].

### 9.2 Secondary Effectiveness Variables

[REDACTED]

[REDACTED]

[REDACTED]

[REDACTED]

[REDACTED]

[REDACTED]

[REDACTED]

## 10.0 EFFECTIVENESS ANALYSIS

Group A and Group B will be analysed and presented separately.

[REDACTED]

The primary analysis will be repeated in the per protocol (PP) population.

[REDACTED]

### 10.1 Primary Effectiveness Analysis

[REDACTED]

[REDACTED]

[REDACTED]

Primary effectiveness analysis (Group A only)

[REDACTED]

[figure not shown]
- a) Non-inferiority will be established if the upper limit of the CI is below the non-inferiority margin of 0.5 units.
- b) Superiority will be declared if the upper limit is below 0.

This decision criteria is consistent with a gate-keeping strategy (testing for superiority following the test for non-inferiority) to maintain the overall type I error rate at 2.5%.

Group B effectiveness success criterion

The CI will be used for assessing non-inferiority in the following way. Non-inferiority will be established if the upper limit of the CI is below the non-inferiority margin of 0.5 units.

## 10.2 Secondary Effectiveness Analysis

## *Effective*

Version: 1.0

Template #: ST-T-002A Ver.: 4.0

Template #: ST  

## Effective

Version: 1.0

Template #: ST-T-002A Ver.: 4.0

Template #: ST  

## 11.0 STATISTICAL/ANALYTICAL ISSUES

### 11.1 Handling of Dropouts or Missing Data

Number of missing values will be summarized and reported as appropriate.

[REDACTED]

Impact of missing data on the primary analysis for Week 12 endpoints will be evaluated by performing sensitivity analysis based on the observed cases in the ITT population.

[REDACTED]

All other effectiveness endpoints will be evaluated based on the observed cases in ITT, i.e. no imputations will be done.

If the adverse event start date is missing, it will be assumed that the AE started on the day of the most recent treatment. Missing stop date for adverse event will not be imputed.

If the adverse event severity assessment is missing, the highest level of severity will be assumed. Missing relationships in adverse event will be imputed as related. AEs will be considered as serious if the assessment on whether the AE is serious or not is missing.

The observed cases in the Safety population will be used for all other safety analysis.

### 11.2 Pooling of Centers in Multi-Center Studies

Pooling of centers might be needed for subgroup analysis based on study site, if there are study sites with few subjects. For Group A, sites with less than or equal to three subjects will be pooled together and for Group B, sites with less than or equal to four subjects will be pooled together.

### 11.3 Multiple Comparisons/Multiplicity

Gate-keeping strategy [REDACTED]  
[REDACTED] is used for adjustments for multiple comparisons or multiplicity.

#### 11.4 Examination of Subgroups

Robustness of the results of the primary endpoint analysis will be investigated across the subgroups of subjects determined by factors according to the exploratory objectives [REDACTED]

To evaluate consistency of AEs across different subgroups, AEs will also be summarized by subgroups [REDACTED]

#### 11.5 Interim Analysis and Data Monitoring

There is no interim analysis planned for this study.

### 12.0 EXTENT OF EXPOSURE

Data of extent of exposure and treatment procedure will be summarized for initial treatment, optional touch-up, and optional re-treatment separately for safety population.

Following parameters will be summarized for left and right side of the midface combined for extent of exposure in Group A:

- Total Volume Injected
- Type of Needle Used
- Injection Depth
- Injection Method

Following parameters will be summarized for left and right side of the midface, separate for the side treated with needle and the side treated with cannula, for extent of exposure in Group B:

- Total Volume Injected
- Injection Tool Used
- Cannula Brand
- Cannula Gauge
- Cannula Length
- Type of Needle
- Type of Cannula
- Injection Depth
- Injection Method

Extent of exposure data will be presented by treatment and subject in data listings.

Following parameters will be summarized for treatment procedure:

- Procedural Anesthetics (No, Yes)
- Type of Anesthetics (Topical, Local Injection, Nerve Block)

- Injection Concomitant Procedures (None, Massage, Ice Pack, Other)

Procedural Anesthetics and Injection Concomitant Procedures data will be presented by treatment and subject in data listings.

## 13.0 SAFETY ANALYSIS

Group A and Group B will be analysed and presented separately. Group A safety analysis will be performed with right and left side of the midface combined. Group B safety results will be summarized separately for the needle and cannula sides of the face (to compare the treatment tools).

The safety endpoints include:

- Evaluation of all adverse events (AEs) including Adverse Events of Special Interest (AESIs).
- Pre-defined, injection related events (IREs) reported during the first 4 weeks after treatment as recorded in the subject diary.
- Evaluation of subject pain for each cheek individually – before (prior to application of anesthetic) and immediately following (before any post-injection procedures) each injection session using an [REDACTED] Numeric Pain Scale (NPS).

- [REDACTED]
- [REDACTED]
- [REDACTED]
- [REDACTED]
- [REDACTED]
- [REDACTED]

### 13.1 Adverse Events

Adverse events (AEs) will be summarized for the safety population. All AEs will be coded using MedDRA and presented by MedDRA system organ class (SOC), preferred term (PT), and treatment.

Only AEs occurring after treatment for subjects will be included in analysis. AEs occurring before, if any, will only be listed in subject data listings. Missing dates, severity, relationship, and seriousness will be imputed as described in section [11.1](#).

All AE endpoints will be summarized for Group A and Group B separately by treatment as follows:

- i) Initial treatment; after their first treatment up until their optional retreatment, or end of study.
- ii) Retreatment; after their optional retreatment up until end of study.

For AE analysis, Touch-up treatment will not be analyzed separately, thus initial treatment + touch-up will be counted as 1 treatment.

Apart from the summary of AEs table described below, all other AE tables will be presented by treatment as follows:

Group A – separate columns for each treatment group.

Group B – one column with AEs associated with side treated with needle, one column with AEs associated with side treated with cannula, and one total column including the total of the first two columns + AEs not associated with any side.

A summary of AEs will be provided, which will include:

- i) number of subjects with at least one AE and number of events (in total as well as serious AEs)
- ii) number of subjects with at least one AE, related to study product or injection procedure, and number of events (in total as well as serious AEs)
- iii) number of subjects with at least one AE, unrelated to both study product and injection procedure, and number of events (in total as well as serious AEs)
- iv) number of subjects with at least one adverse events of special interest (AESI), and number of events (in total as well as serious AEs)
- v) number of subjects who did not have an AE

Summary of AEs table will be presented by treatment for Group A.

For Group B, this summary table will be presented in one total column. In addition, there will be one row for AEs related to side treated with needle, one row for AEs related to side treated with cannula, and a row for AEs related but not to a specific treatment area.

AEs will be summarized by SOC, PT, and severity.

The number of subjects with AEs related to study product or injection procedure as well as the number of events will be summarized by SOC, PT, and severity.

The number of subjects with AEs unrelated to both study product and injection procedure as well as the number of events will be summarized by SOC, PT, and severity.

In addition, for related AEs, the number of days to onset and the duration of event will be summarized by SOC and PT using mean, SD, min, max and median.

Time to onset of an AE will be derived as the start date minus the date of most recent treatment. If the start date is missing, it will be assumed that the AE started on the day of most recent treatment.

Duration of an AE will be derived as the stop date minus the start date + 1. If the start date is missing, it will be assumed that the AE started on the day of most recent treatment. Missing stop date will not be imputed and therefore no duration will be calculated in these cases. Instead, the number of AEs that were ongoing at the end of the study will be given.

If a subject has more than 1 AE of the same PT and there are different grades of severity, only the highest grade will be represented in the summary of severity.

Action taken for related AEs will also be summarized.

To evaluate consistency of the results across different subgroups, AEs will also be analyzed across different subgroups as described in the exploratory objectives (see Section 3.1.4) using a table with related AEs by SOC, PT and severity.

Hypertrophic scarring/hyperpigmented scarring will be summarized by FST I-III, IV, and V-VI.

Incidences of visual disturbances are considered Adverse Events of Special Interest (AESIs) and include but are not limited to the following: loss of vision, blurry vision, double vision, pain in or around the eye, blind spot or shadow in the visual field, trouble moving eyes, etc.

All reported AEs will be listed in data listings including time to onset, duration of AE and timing of the AE. Timing would be the variable indicating whether the AE occurred after no treatment, initial treatment, or optional retreatment.

By-subject listings also will be provided for all subjects (safety population) for the following: AEs related to study product or injection procedure, AEs resulting in discontinuation of study product, serious AEs, and AESIs. Adverse events with late onset (onset >21 days) will be provided in a listing.

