### 3.3 Treatments and Assignment to Treatments

Subjects will be enrolled in two groups – Group A and Group B.

**Group A:** Approximately 210 subjects, over the age of 21, will be randomized in a 2:1 ratio, to receive treatment with either GAL1704 or Juvéderm Voluma® XC, respectively. Approximately 140 subjects will be treated with GAL1704 and 70 subjects will be treated with Juvéderm Voluma® XC.

[REDACTED]  
sites will have a BE, blinded to the treatment provided to each subject, who will perform the blinded assessments.

**Group B:** An additional 60 subjects will be enrolled and treated with GAL1704 only. These subjects will be treated using a split face design, i.e., one cheek will be treated using a small blunt tip cannula and the other cheek will be treated using the co-packed needle.

[REDACTED]  
[REDACTED] The Treating Investigator will not be blinded to study treatments and will administer the treatments to each subject. Safety assessments will be performed by non-blinded personnel.

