## 5.0 ANALYSIS POPULATIONS

The Analysis Populations are defined separately for Group A and Group B as described below.

- **Safety Population:** Includes all subjects who were injected at least once. Subjects are analysed according to the treatment they actually received.

- **Intention-to-Treat (ITT) Population:** Includes all subjects who were randomized. Subjects are analysed according to the treatment they were randomized to.
- **Per-Protocol (PP) Population:** Includes all subjects in ITT who complete the Week 12 visit without any deviations considered to have substantial impact on the primary effectiveness outcome.

Safety population will be the basis for all safety evaluations. When performing effectiveness analysis, the ITT population will be used. Primary effectiveness analysis will be repeated using the PP populations. Additional endpoints maybe explored in the PP population if deemed necessary.

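### Does the Group B total column in the adverse event tables count subjects with events on both cheeks twice?

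*SAP*

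**What the plan says.** SAP 3.3 describes Group B: "An additional 60 subjects will be enrolled and treated with GAL1704 only", and in each of them "one cheek will be treated using a small blunt tip cannula and the other cheek will be treated using the co-packed needle". Every Group B subject can therefore have events in either side column or in both.

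SAP 13.1 sets three columns for Group B: AEs associated with the needle side, AEs associated with the cannula side, and "one total column including the total of the first two columns + AEs not associated with any side". The scope of this layout is limited: "Apart from the summary of AEs table described below, all other AE tables will be presented by treatment as follows". These tables are broken down by SOC, PT and severity, and they report both subjects and events. For related AEs the text is "The number of subjects with AEs related to study product or injection procedure as well as the number of events will be summarized"; unrelated AEs are treated the same way.

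The summary table is laid out differently. For Group B it has a single total column, with the sides shown as extra rows. It gives subjects with at least one AE separately from events, overall and for related, unrelated and special-interest AEs, each with serious AEs shown. It also gives the "number of subjects who did not have an AE".

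Two other provisions bear on the point. The safety population "Includes all subjects who were injected at least once", so the unit is the person. SAP 13.1 also says that a subject with several AEs of one PT at different grades appears in the severity summary at the highest grade only.

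**The concern.** The needle and cannula columns are drawn from the same people. Event counts from the two sides can be added if each event belongs to one side. Subject counts from overlapping sets cannot. The wording of the total column resembles a sum, and SAP 13.1 contains no sentence saying that a subject counts once in it.

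A programmer who added the subject counts across columns would overstate Group B incidence in the SOC and PT rows, and for common events could exceed the number of subjects treated. Those rows would not be comparable with Group A, where SAP 13.0 combines the two sides of the face, and they could disagree with Group B's own summary table.

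**Working it through.** The plan states no AE rate, no overlap between cheeks and no expected Group B incidence, so there is no figure to reproduce. The check has two parts: what adding the columns would do, and whether the text asks for it.

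**Size if subject counts were added.** N = 60 (SAP 3.3). The per-side proportion p, equal on both sides, and the overlap are assumptions.

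- Column sum: n_needle + n_cannula = 2pN.
- Distinct subjects: n_needle + n_cannula − n_both.
- Independent sides: N × [1 − (1 − p)²], so the ratio of sum to distinct is 2p / [1 − (1 − p)²] = 2 / (2 − p).
- Complete overlap: pN, ratio 2. No overlap: ratio 1.

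| p per side (assumed) | Column sum | Distinct, independent sides | Ratio | Distinct, complete overlap | Ratio |
|---|---|---|---|---|---|
| 5% | 6 (10%) | 5.9 (9.8%) | 1.03 | 3 (5%) | 2 |
| 20% | 24 (40%) | 21.6 (36%) | 1.11 | 12 (20%) | 2 |
| 50% | 60 (100%) | 45 (75%) | 1.33 | 30 (50%) | 2 |
| 60% | 72 (120%) | 50.4 (84%) | 1.43 | 36 (60%) | 2 |

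An example with non-side events, also assumed: needle 12, cannula 12, both 8, non-side 6, of whom 2 also have a side event. The sum is 12 + 12 + 6 = 30 (50%). Distinct subjects are 12 + 12 − 8 + 6 − 2 = 20 (33%).

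**Whether the text asks for it.**

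1. The first two columns are defined as holding AEs associated with a side, and the remainder as AEs associated with no side. All three components are sets of events. Their total is the set of all Group B AEs, from which the number of events and the number of subjects are each counted. Nothing says that subject counts are added.
2. Take a subject with a mild event on the needle side and a moderate event of the same PT on the cannula side. Adding columns puts that person in both the mild and the moderate rows of the total. The highest-grade rule allows only the moderate row. Pooling the events first satisfies the rule.
3. In the summary table, subjects with an AE and subjects without one must add up to the Group B safety population. That holds only for distinct people. A count of 72 among 60 would leave 60 − 72 = −12 without an AE. The table is outside the three-column layout, so overall, related, unrelated, serious and special-interest incidence do not depend on the disputed wording.
4. SAP 13.1 has no count-once sentence for Group A either. A number of subjects with AEs is still read there as a number of people, and the same reading serves for Group B.

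**The case for a change.** The best case for a change is that the SAP does write a count-once rule where it wants one: SAP 13.12 states it for concomitant medications. It is absent from 13.1, where the split-face layout makes it more useful. The highest-grade rule does not say whether it works within a side or across sides, and it does not mention two events of equal grade. There is no class for an AE recorded on both cheeks, so if one such record appears in both side columns, adding them double counts the event as well as the person. One sentence would settle all of this.

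The observations are correct, but they establish silence and not a wrong instruction. The highest-grade rule is written per subject with no reference to side, so in a column covering both sides its plain application is across sides. An AE on both cheeks counts as one subject under pooling, whether it is entered as one record or two. Only its event count depends on how it is recorded. SAP 15.0 provides for table mock-ups and clarifying footnotes, a normal place for such a convention.

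Bruising or similar reactions are also an uncertain illustration. Pre-defined post-treatment events are collected in the diary and displayed separately from other AEs (SAP 13.2), and the documents available do not show which symptoms are on that list.

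**Conclusion.** No change to the plan is needed. What remains is a gap in detail, confined to the subject counts in the Group B total column of the tables by SOC, PT and severity. The natural reading, and the one consistent with the rest of SAP 13.1, is a count of distinct subjects among the pooled AEs. Under it there is no overstatement.

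If the columns were added instead, the two sides alone would inflate a row by a factor between 1 and 2, and overlap with non-side events would add to that. Where any row would fall cannot be derived from the documents, since every rate and overlap used above is assumed. Event totals are right under either reading if each event belongs to one side.

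The tables are descriptive and no test or decision rule rests on them. The needle and cannula columns, which serve the comparison of injection tools named in SAP 13.0, are unaffected. The conclusion assumes that the analyst counts people when a table asks for a number of subjects, which is standard practice. A footnote on the table mock-up would be harmless, but the plan does not depend on it.

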4.4.2 Blinding

The Treating Investigator will not be blinded to study treatments.

[REDACTED] The BE will remain blinded to subject randomization and treatment and will perform the blinded assessments as specified in the SOE.

[REDACTED]

[REDACTED]

Safety assessments will be performed by non-blinded site personnel who are qualified by training and experience.

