8.1 Assessment of AEs by direct question to subject and evaluation of subject

Safety evaluations for this study include an interview of the subjects at each visit to obtain information about any medical occurrence that meets the definition of an AE. Each subject should be questioned about AEs at each study visit following the screening visit. The question asked should be asked: "Since your last clinical visit have you had any health problems?" Information on AEs can also be obtained from signs and symptoms detected during each examination by the Investigator or designee, which should include visual inspection of the treatment area.

AEs must be documented in the source document and eCRF without regard for cause or relation to investigational product. If in the process of the interview, additional information regarding medical history or pre-planned medical or surgical procedures is revealed, it must be documented in the source document(s) and eCRF.

It is the responsibility of the Investigator to determine severity of the AE and relatedness of the event to the study product.

[REDACTED]

[REDACTED]

[REDACTED]

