8.6.3 Recording instructions

AEs will be recorded once a subject is enrolled (i.e., randomized and/or treated) in the study. All other events that occur after the subject signs the ICF but before enrollment will be recorded in the subject's medical history. Each AE should be fully recorded in the subject's source document and the eCRF. Beginning after initial treatment on Day 1, each subject should be questioned about AEs at each study visit. The question asked should be: "Have you had any health problems since receiving study treatment?" Information on AEs can also be obtained from signs and symptoms detected during each examination.

When an AE is related to a device deficiency including technical device malfunction, the AE should be recorded in the AE eCRF and the technical complaint should be reported separately on the study complaint form.

Investigators, or other study site personnel, shall record all AEs in the eCRF, including:

- a) Event term (recorded in standard medical terminology and avoiding abbreviations)
- b) Description of event and affected area
- c) Start date (first day with symptoms)
- d) Stop date (last day with symptoms)
- e) Intensity (mild, moderate, or severe according to definition in Section 8.6.3.1)
- f) Seriousness (serious or not serious, according to definition in Section 8.6.3.2)
- g) Causal relationship to study product or study product injection procedure (yes or no)
- h) Action taken (none, medication treatment, non-medication treatment, or other procedures/tests, subject withdrawn)
- i) Outcome of the AE (ongoing, recovered, recovered with sequelae, death, chronic/stable, not recovered at the end of the study)

The pre-defined, expected post-treatment events shall be assessed separately. These events shall be collected daily by subjects in a Diary for up to 28 days after each treatment.

⁸ Planned hospitalisation for a pre-existing condition, or a procedure required by the CSP, without serious deterioration in health, is not considered a SAE. (Source: ISO14155:2011).

8.6.3.1 *Intensity*

Intensity will be recorded for each reported AE. The following definitions of intensity are to be used:

Mild: Awareness of symptoms or signs, but easily tolerated (acceptable)

Moderate: Enough discomfort to interfere with usual activity (disturbing)

Severe: Incapacity to work or to do usual activity (unacceptable)

If the intensity changes within one day, the maximum intensity of the AE during that day shall be recorded.

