8.6.3.2 *Causal relationship and seriousness*

Each AE, serious as well as non-serious, shall be assessed by the Investigator for causal relationship with the study product and its use (the injection procedure) and for seriousness (Yes or No) of the event.

A two-point scale (Yes or No response) shall be used for the causality assessments. The Investigators shall be asked to indicate a response to each of the following questions in the eCRF:

- “Do you consider that there is a reasonable possibility that the event may have been caused by the study product?”, and
- “Do you consider that there is a reasonable possibility that the event may have been caused by the device injection procedure?”

If any of these questions is answered ‘Yes’, the AE is considered related.

Each AE will also be assessed for causal relationship and seriousness by the Sponsor, in order to fulfil regulatory requirements.

8.6.4 *Reporting of adverse events*

Adverse event reporting on each subject shall start upon enrollment (i.e., randomized and/or treated with study product) in the study. Any events that occur after the subject signs the ICF but before enrollment will be recorded in the subject’s medical history. The reporting shall continue during each follow-up visit (including telephone contacts and unscheduled visits) until the last scheduled visit in the study.

All AEs, non-serious as well as serious, are to be reported as an AE in the eCRF.

8.6.5 *Reporting of adverse events of special interest (AESIs)*

AESIs should be reported (using the AE Clarification Form) within 24 hours of awareness to the Sponsor/CRO at the email address [REDACTED]. In case of difficulty to obtain all the required information within 24 hours, an initial report can be submitted with follow up information provided within 24 hours of awareness of the new information.

The following information should be provided when reporting an AESI:

- Subject identification (subject number and initials)
- Event description including observed symptoms

- Medical history related to event
- Event onset date and time
- Depth of injections
- Interventions implemented to treat event
- Event outcome (with resolution date and time if applicable)
- Relatedness to study product or procedure
- Seriousness of event
- Study treatment information (number of injections, date of injections, name of product injected, volume injected, etc.)

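### Group A onset, duration and action-taken summaries cover only AEs called related, a judgement probably made knowing the arm; add the same summaries for all post-treatment AEs

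*SAP*

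**What the plan says.** SAP 13.1 plans several AE outputs. In Group A, all of them are shown by treatment arm.

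- Counts of subjects and events, and tables by SOC, PT and severity, are planned for all AEs, for related AEs and for unrelated AEs.
- Onset and duration are narrower: "In addition, for related AEs, the number of days to onset and the duration of event will be summarized by SOC and PT". The statistics are mean, SD, minimum, maximum and median.
- Action taken is narrower too: "Action taken for related AEs will also be summarized".
- The AE subgroup check is done "using a table with related AEs by SOC, PT and severity".
- Onset and duration for every AE appear in a listing. AEs with onset after 21 days get their own listing.

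On who decides what counts as related, Protocol 8.1 says: "It is the responsibility of the Investigator to determine severity of the AE and relatedness of the event to the study product". Protocol 8.6.3.2 repeats it: "Each AE, serious as well as non-serious, shall be assessed by the Investigator for causal relationship with the study product". There are two yes/no questions, one on the product and one on the injection procedure, and "If any of these questions is answered ‘Yes’, the AE is considered related".

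On blinding, Protocol 4.4.2 leaves the Treating Investigator unblinded and adds: "Safety assessments will be performed by non-blinded site personnel who are qualified by training and experience". SAP 3.3 agrees. Only the blinded evaluator's assessments are described as blinded.

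**The concern.** Randomization protects a comparison of all events that follow treatment. It does not protect a comparison of events picked out afterwards by an opinion that may depend on the arm. Group A compares an investigational product with a marketed one, and the person judging causality probably knows which was injected. A late or prolonged event might be attributed to treatment more readily in one arm than in the other. The related-only onset, duration and action-taken summaries would then describe differently selected events, and a reader comparing the columns could take a difference in attribution for a difference between products.

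What is at stake is the reading of three descriptive safety summaries. The primary effectiveness analysis and the overall AE incidence tables do not use this filter.

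**Working it through.** The plan gives no figure to reproduce here. The check has three parts: which outputs lack an unfiltered counterpart, whether the filter could depend on the arm, and whether such a filter can create a difference from nothing.

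**1. Which outputs have an unfiltered counterpart (readable text of SAP 13.1)**

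| Output | Related AEs | All AEs | Unrelated AEs |
|---|---|---|---|
| Subject and event counts | by arm | by arm | by arm |
| SOC, PT, severity | by arm | by arm | by arm |
| Onset and duration | by arm | listing only | listing only |
| Action taken | by arm | no summary | no summary |

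The gap is in the last two rows.

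**2. Can the filter depend on the arm?** The causality call belongs to the Investigator (Protocol 8.1, 8.6.3.2). The protocol's definitions make that the PI or a delegated sub-investigator, and do not say that this is the Treating Investigator. But the Treating Investigator is unblinded and safety assessments are done by non-blinded staff (Protocol 4.4.2, SAP 3.3). Unblinded causality is the most likely reading, though not an explicit statement. The Sponsor also assesses causality for regulatory purposes, but the readable SAP gives that assessment no role in these tables.

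**3. Duration, on assumed values.** In both arms 70% of events last 5 days and 30% last 40 days. Short events are called related 90% of the time in both arms; long events 90% in arm X and 60% in arm Y. The documents give none of these values.

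- Mean related duration = (sum of share × call rate × days) / (sum of share × call rate).
- Arm X: (0.7×0.9×5 + 0.3×0.9×40) / (0.63 + 0.27) = 13.95 / 0.90 = 15.5 days.
- Arm Y: (0.7×0.9×5 + 0.3×0.6×40) / (0.63 + 0.18) = 10.35 / 0.81 = 12.8 days.
- Without the filter, both arms: 0.7×5 + 0.3×40 = 15.5 days.
- Short events as a share of related events: 0.63/0.90 = 70.0% and 0.63/0.81 = 77.8%. The median is therefore 5 days in both arms, with minimum 5 and maximum 40. Only the mean and SD move.

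**4. Onset, on a second set of assumed values.** In both arms 70% of events are early (mean onset 3 days; 95% called related) and 30% are late (mean onset 90 days). Late events are called related 10% of the time in one arm and 30% in the other.

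- (0.665×3 + 0.03×90) / 0.695 = 6.8 days.
- (0.665×3 + 0.09×90) / 0.755 = 13.4 days.
- Without the filter, both arms: 0.7×3 + 0.3×90 = 29.1 days.
- With late-event call rates of 20% and 30%, the means are 10.2 and 13.4 days, a gap of 3.2 days.
- Keeping 10% and 30% but varying the early share from 50% to 90%, the gap runs from 12.6 days (11.3 and 23.9) to 1.9 days (4.0 and 5.9).
- With equal call rates in the two arms, the gap is zero.

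**5. Action taken.** In step 3, long events make up 0.27/0.90 = 30.0% of related events in arm X and 0.18/0.81 = 22.2% in arm Y. If long events are treated more often than short ones, the action-taken distribution shifts in the same way.

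**The case against.** The case for leaving the plan alone has real force.

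- **Other tables would expose an attribution difference.** A reader might infer that nothing planned could reveal it. The documents do not support that. By-arm related and unrelated counts, and tables by SOC, PT and severity for all, related and unrelated AEs, would show it if one arm's events were more often called unrelated. This stands for incidence and severity. It does not supply an unfiltered summary of onset, duration or action taken.
- **The any-Yes rule narrows the mechanism.** Both Group A arms are injected by needle, so a cheek reaction can qualify through the procedure question alone. Missing relatedness is imputed as related. This stands for early local reactions. Late or prolonged events leave more room for judgement, and they carry most weight in a mean.
- **The median is robust in the duration example.** This stands, as long as long events are a minority. The plan is also by SOC and PT, whereas the example pools all events.
- **Diary events bypass the filter.** Subjects record the pre-defined reactions for up to 28 days after each treatment, and number of days is summarised. This stands for that window only; participation can last up to 74 weeks.
- **The tables are descriptive.** The readable text plans no test on them. This stands, and it limits the severity.

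A reader might also infer that the related-only subgroup table is biased. The documents do not show this. Attribution that differs by arm but equally in every subgroup would not in itself make subgroups look inconsistent, and the subgroup definitions are redacted.

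**Conclusion.** The point holds as a minor one. The Group A onset, duration and action-taken summaries rest on events selected by a judgement most likely made with knowledge of the arm, and no readable text plans the same summaries without that selection. If attribution differs by arm, means and the action-taken distribution can differ where true events do not. The assumed cases give 15.5 against 12.8 days for mean duration (12.8 is about 18% below 15.5), with an unchanged median, and 1.9 to 12.6 days for mean onset.

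These sizes rest wholly on the assumed call rates and event mixes. A reader might infer that attribution will favour one product. The documents give no evidence that it will differ, and none on direction. Overall AE incidence and severity, and the primary analysis, are not affected.

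**What to change.** In SAP 13.1, add Group A summaries by arm of time to onset, duration and action taken, by SOC and PT, for all post-treatment AEs regardless of causality. State that differences between arms are read from these, and keep the related-only tables as supportive.

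Two additions are optional:

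- A version restricted to events in the treated midface, where the recorded data allow it. This should not be the main base. The eCRF item is "Description of event and affected area", which is descriptive and not shown to be a coded location. A location filter could also drop the visual disturbances that SAP 13.1 names as AEs of special interest.
- The AE subgroup table run on all AEs as well.

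No new data are needed, because Protocol 8.6.3 already collects start date, stop date and action taken for every AE. The cost is SAP wording and modest programming. The downside is that some events unrelated to treatment enter the new tables and may dilute a real difference, which is a reason to keep the related-only versions beside them.
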